# 1. Protocol Summary

## 1.1 Synopsis

Title	A Follow-up Trial of Proglucamune® in the Treatment of Protective Qi Insufficiency, a TCM Condition
Study Description:	In this protocol, we will developed a novel, evidence-based approach to test the hypothesis that $\beta$ -glucan enhances Protective Qi (PQi), an important TCM concept which stipulates that a protective force circulates throughout the body surface and works as the first line of defense of against “external pernicious influences (外邪)”.
Objective:	The primary objective of this study is to re-test the beneficial effects of Reishi for its Protective Qi (PQi) enhancing and immune-modulating effects in a double-blind, placebo-controlled study. The secondary objective of this study is to determine the effect of Proglucamune® on strengthening General Qi (GQi).
Endpoints	The primary endpoint is the change of PQi Deficiency (PQD) status accessed by a standardized multifactorial severity score and traditional method. The secondary endpoint is the change of GQi Deficiency (GQD) status accessed by a standardized multifactorial severity score and traditional method, the change of Global Health, Emotional Impact, Saliva sIgA, and Emotional and Behavioral Dyscontrol.
Study Population	130 male or females aged 18 to 65 will be enrolled without regard to race or ethnic background. All subjects should be generally healthy but exhibit an PQi Insufficiency score >1.8 (an empirical threshold derived from preliminary study that allows increased responsiveness to beta glucan).
Description of Sites/Facilities Enrolling Participants:	This study will be conducted at the Elegant and Olive Health Clinic, [name]. Subjects for this study will be recruited through investigators of this trial, referral from other TCM practitioners, or via advertisement.
Description of Study Intervention:	Participants will be treated with 2 tablets of Proglucamune per day (containing 200mg of beta glucan).
Study Duration:	24 months
Participant Duration	3 months

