## 3. Objectives and Endpoints

Objective	Endpoints	Justification for endpoints
Primary		
To test $\beta$ -glucan enhances Protective Qi (PQi)	
 
• PQi Deficiency (PQD) status accessed by a standardized multifactorial severity score
 
• PQi Deficiency (PQD) status accessed by a traditional method
 
	
We have previously created and validated standardized score for assessing PQD severity.
 
The traditional diagnosis method is also used as an additional way to evaluate the treatment.

Secondary		
To evaluate the effect of $\beta$ -glucan on GQi severity score, salivary IgA, general health status through Patient-Reported Outcomes Measurement Information System (PROMIS), Emotional Impact, and Emotional, and Behavioral Dyscontrol.	
 
• GQi Deficiency (GQD) status accessed by a standardized multifactorial severity score
 
• GQi Deficiency (GQD) status accessed by a traditional method
 
• Global Health - Physical
 
• Global Health – Mental
 
• Emotional Impact
 
• Saliva sIgA
 
• Emotional and Behavioral Dyscontrol
 
	
PQi is a component of GQ, <math>\beta</math>-glucan may improve GQi, too.
 
Salivary IgA is a biomarker of immune. <math>\beta</math>-glucan's effect on immune defense may affect Salivary IgA.
 
The improvement of PQi can be accompanied by improved life quality.
 
Patient-Reported Outcomes Measurement Information System (PROMIS), Emotional Impact, Emotional and Behavioral Dyscontrol will be collected to evaluate the improvement of participants' life quality.

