## 4. Study Design

## **4.1 Overall Design**

The objective of this study is to expand upon our previous findings and, more specifically, to re-test our hypothesis in a triple-blind, placebo-controlled study with n=62 subjects in both the intervention (Proglucamune®) and placebo treatment groups. In addition, since TCM literature indicates that Reishi not only increases PQi but also the level of Qi in general (i.e., general Qi, GQi), and since PQi is a component of GQ, the secondary objective of this study is to determine the effect of Proglucamune® on strengthening GQi.

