## **9. Statistical Considerations**

### **9.1 Statistical Hypotheses**

- **Primary Efficacy Endpoints:**
  - Change of Protective Qi after a total of 12 weeks follow-up
- **Secondary Efficacy Endpoints:**
  - Change of Generic Qi after a total of 12 weeks follow-up
  - Change of Global Health (Appendix 5) including physical health and mental health after a total of 12 weeks follow-up
  - Change of saliva secretory IgA after a total of 12 weeks follow-up
  - Change of Emotional and Behavioral Dyscontrol (Appendix 6) after a total of 12 weeks follow-up
  - Change of Emotional Impact (Appendix 7) after a total of 12 weeks follow-up

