#### **9.4.2 Analysis of the Efficacy Endpoint(s)**

Trial outcome measures, if they are continuous, will be evaluated by skewness and kurtosis for normality and expressed as mean (95% CI) if both measures were within the range of (2, -2); otherwise they will be expressed as median (95% CI) with specification. Given the potential effect of treatment time on trial outcomes, we will analyze the effect of  $\beta$ -glucan with adjustment by treatment time. This will be conducted by linear mixed regression [16] or Aligned Rank Transformation ANOVA [17] if assumptions of the regression model were not satisfied. Categorical outcomes will be derived from conventional PQD diagnosis. The effect of  $\beta$ -glucan will be analyzed using generalized mixed linear model [18] for conventional PQD diagnosis.

For all statistical analyses, differences with a  $P < 0.05$  (two tailed) will be considered significant.

Other details analysis of the primary endpoints are described as follows:

- The PQi status of each participant at baseline and each follow-up visit will be measured by on-site investigators (licensed TCM practitioners) through a standardized quantitative assessment (Table 1 & Table 2). Each health condition relevant to PQD (i.e. cold frequency, symptoms, and signs) will be scored on a designed scale (ranging 1-10, with higher number indicating more severe deficiency) based on a set of standardized and specified criteria (Table 2). The sub-scores are then weighted (cold history 25%, symptoms 33.3%, signs: 41.7%) to arrive at a final PQD severity score. This score is on a 1-5 scale, with 5 being the most severe deficiency. The change of the score from baseline, indicating the treatment effect, will be calculated and analyzed by statistical means.
- PQi status of each participant at baseline and each follow-up visit will be measured by on site-investigators (licensed TCM practitioners) through non-standardized, qualitative traditional assessment. The status was characterized by non-PQD or PQD. The change of PQi status from baseline, indicating the treatment effect, will be calculated and analyzed by categorical statistic.

Other details analysis of the secondary endpoints are described as follows:

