- The GQi status of participants at baseline and each follow-up visit will be assessed by on-site investigators (licensed TCM practitioners) through a standardize quantitative assessment (Table 3 & Table 4). Each health condition relevant to GQi Deficiency (GQD) (including symptoms, and signs) will be scored based

on a standardized criteria (Table 4), and then weighted to arrive at a final GQi severity score (Table 3). This score is on a 1-5 scale, with 5 being the most severe deficiency. The change of the score from baseline, indicating the treatment effect, will be calculated and analyzed by statistical means.

- The participants' Global Health will be assessed using the established PROMIS® Scale v1.2 (Please see the link <https://www.healthmeasures.net/explore-measurement-systems/promis> ). This questionnaire consists of 10 global-health related questions. The answer for nine of ten questions are graded on 1-5 scale (with 5 being the best), and one question is graded on 1 to 10 scale (with 10 being the worst grade). The sub-scores are used to obtain a final combined score of Global Physical Health or Global Mental Health using a T-score metric in which 50 is the mean of a relevant reference population and 10 is the standard deviation (SD) of that population. The change of the score from baseline, indicating the treatment effect, will be calculated and analyzed by statistical means.
- The effect of Proglucamune on the participants' immunity will be assessed by the change of saliva secretary IgA, which will be normalized by the secretion rate ( $\mu\text{g}/\text{min}$ ). The change of the score from baseline, indicating the treatment effect, will be calculated and analyzed by statistical means.
- Neuro-QoL (Quality of Life in Neurological Disorders) is a measurement system that evaluates and monitors the physical, mental, and social effects experienced by adults and children living with neurological conditions. Please see the link (<http://www.healthmeasures.net/explore-measurement-systems/neuro-qol>) for details. This questionnaire consists of 8 questions related to emotional and behavioral control. The answers for each of the questions are graded on five levels from best to worst. A combined score is generated using a T-score metric in which 50 is the mean of a relevant reference population and 10 is the standard deviation (SD) of that population.

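### Seven secondary endpoints share one uncorrected two-tailed 0.05 rule: with no true effect, the chance of at least one significant difference in either direction is about 23% (15-30%), and of at least one false benefit about 11.5% (7-16%)

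*Combined protocol and SAP*

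**What the plan says.** All references are to the combined protocol and SAP.

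- **Decision rule.** Section 9.4.2 applies one criterion to every analysis: "P < 0.05$ (two tailed) will be considered significant". It makes no exception for secondary endpoints.
- **Endpoint list.** Section 3 gives seven secondary bullets: the General Qi deficiency (GQD) severity score, "GQi Deficiency (GQD) status accessed by a traditional method", Global Health physical, Global Health mental, Emotional Impact, salivary sIgA, and Emotional and Behavioral Dyscontrol. The Synopsis (1.1) agrees that General Qi is measured in two ways: "The secondary endpoint is the change of GQi Deficiency (GQD) status accessed by a standardized multifactorial severity score and traditional method".
- **A shorter list.** Section 9.1 has five secondary bullets. One covers two outcomes: "Change of Global Health (Appendix 5) including physical health and mental health after a total of 12 weeks follow-up". Another is "Change of saliva secretory IgA after a total of 12 weeks follow-up". Traditional GQD is not a separate item there.
- **Priority.** Section 4.1 names a single secondary objective: "the secondary objective of this study is to determine the effect of Proglucamune" on General Qi. The Synopsis also names General Qi alone as the secondary objective.
- **Analysis.** For the GQD score, Global Health and sIgA, 9.4.2 repeats one sentence: "The change of the score from baseline, indicating the treatment effect, will be calculated and analyzed by statistical means". It names a categorical model only for the conventional Protective Qi (PQD) diagnosis, so traditional GQD has no stated model.

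No section gives a testing order, an alpha split, a gate on the primary endpoint, or an exploratory label for the secondaries.

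**The concern.** The secondary endpoints concern different things: General Qi, immune status through sIgA, and quality of life through the questionnaires. Under the rule as written, a report could call an effect on any of them significant because that one test crossed 0.05, even if the primary endpoint failed and the other secondaries showed nothing. The reader would see a 5% standard applied test by test, while the chance that something in the secondary list crosses it by luck is several times higher. The plan states an order of importance, with General Qi first, but the decision rule does not use it.

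This point concerns the secondary family only. How the two primary measures relate to each other matters here only because a gate needs a named primary analysis.

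**Working it through.** **1. The plan's own figures.** The documents state no familywise error rate, so there is none to reproduce. The only other alpha is in section 9.2: 0.01, with power 0.9 and effect size 0.8. A two-sample, two-sided t-test with these inputs needs 48.19 per group, rounded up to 49, which matches the plan. Allowing for the 20% attrition in section 7.2.2, 49 / 0.8 = 61.25, rounded up to 62, which matches section 4.1. The 0.01 therefore sized the trial; the decision rule in 9.4.2 is 0.05.

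**2. Inputs.**
- Per-test level: 0.05 two-tailed (9.4.2), critical value c = 1.96. With no effect, each test gives a significant difference 5% of the time and a significant benefit 2.5% of the time.
- Number of endpoints k: 7 (section 3); 6 or 5 (section 9.1, with Global Health split or not).
- One test per endpoint: assumed.
- Correlation ρ between test statistics: not in the documents. A common value is assumed, 0.5 as the centre and 0 to 0.8 as the range.

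**3. Independent tests.**
- Either direction: 1 − 0.95^7 = 30.2%.
- Benefit only: 1 − 0.975^7 = 16.2%.

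**4. Correlated tests.** Write each statistic as Z_i = √ρ·X + √(1−ρ)·e_i, with X and the e_i independent standard normal, and Φ the standard normal distribution function. Then

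- either direction: 1 − E{[Φ((c − √ρX)/√(1−ρ)) − Φ((−c − √ρX)/√(1−ρ))]^k}
- benefit only: 1 − E{[Φ((c − √ρX)/√(1−ρ))]^k}

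where the expectation is over X, found by numerical integration.

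| ρ | k = 7, either | k = 7, benefit | k = 6, either | k = 6, benefit |
|---|---|---|---|---|
| 0 | 30.2% | 16.2% | 26.5% | 14.1% |
| 0.3 | 27.2% | 13.7% | 24.1% | 12.2% |
| 0.5 | 23.0% | 11.5% | 20.7% | 10.4% |
| 0.7 | 17.8% | 8.9% | 16.4% | 8.2% |
| 0.8 | 14.9% | 7.4% | 13.9% | 6.9% |

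Counting only the five bullets of section 9.1 gives 22.6%, 18.3% and 12.7% in either direction at ρ = 0, 0.5 and 0.8.

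**5. Unequal correlations.** The assumed structure is: the GQD pair 0.7, the four patient-reported scales 0.5 with each other, 0.25 between these two blocks, and sIgA 0.05 with everything. Simulation with seven endpoints then gives 25.9% in either direction and 13.2% for benefit, inside the ranges above.

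**6. Size relative to a single test (k = 7).** Either direction: 14.9/5 = 3.0 to 30.2/5 = 6.0 times. Benefit: 7.4/2.5 = 3.0 to 16.2/2.5 = 6.5 times.

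**The case against.** - **Secondary endpoints are usually read as supportive.** No section makes success on any one of seven a criterion for the trial, and section 3 presents quality of life as something that may accompany a Protective Qi improvement. It is true that the any-one-of-seven rate is not a quantity the plan defines. But the documents never call the secondaries supportive or exploratory, and the rule in 9.4.2 covers every analysis. If nominal reporting is what was meant, the plan should say so.
- **The count of seven is not secure.** This stands in part. Section 9.1 supports five or six, and traditional GQD has no stated model. The smaller counts reduce the figures without changing the conclusion: even five endpoints at ρ = 0.8 give 12.7%, about 2.5 times 5%.
- **The endpoints are correlated.** Allowed for, up to ρ = 0.8.
- **The trial used alpha 0.01.** Only for the sample size, so it does not protect the secondary tests.
- **A stronger reading.** A reader might infer that an ineffective product has a 23% chance of showing a significant secondary benefit. The plan does not support that. The tests are two-tailed, so the 23% includes results in which the product looks worse than placebo. The benefit figure is about half, 11.5%, and even independent endpoints reach only 16.2%.
- **Some of the remedy already exists.** Correct: 9.4.2 already reports continuous outcomes with 95% confidence intervals. What is missing is a rule on which of them may carry a claim.

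**Conclusion.** The concern holds. The secondary endpoints fall under a single uncorrected two-tailed 0.05 rule, with no order, gate or label. With seven endpoints, no true effect and a common correlation of 0.5, the chance of at least one significant secondary difference in either direction is about 23% (15-30% for ρ from 0.8 to 0), and of at least one false benefit about 11.5% (7-16%). The single-test figures are 5% and 2.5%. With six endpoints the chances are about 21% (14-26%) and 10% (7-14%).

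The absence of any control is established from the text. The percentages rest on assumed correlations and one test per endpoint; testing further visits separately would raise them. The change should be made, but it affects secondary claims only and does not threaten the primary analysis.

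**What to change.** In section 9.4.2:

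1. Limit the P<0.05 rule to the primary analysis and one gated secondary test.
2. Test the week-12 GQD severity score at two-sided 0.05 only if a named primary analysis is significant. The name is needed because the Synopsis and section 3 give two primary measures, so a gate on the primary in general would be undefined. The week-12 PQD severity score is one candidate. Putting General Qi first follows the priority in sections 1.1 and 4.1.
3. Report the remaining secondaries (traditional GQD, both Global Health scores, sIgA, Emotional Impact, Dyscontrol) as exploratory, with estimates, 95% confidence intervals, nominal P values and no significance claim. If formal claims on them are wanted, apply Holm across these six after GQD succeeds. Its strictest step is 0.05/6 = 0.0083. At the plan's effect size of 0.8, a two-sample t-test at that level has 89% power with 49 per group and 96% with 62; smaller effects would have less.
4. Make the lists in sections 3 and 9.1 agree, and state a model for traditional GQD.
5. If data were already unblinded when the rule is added, disclose that. Version 4.0 is dated February 2022 and section 5.5 planned enrollment to end in March 2019, but the documents do not say whether unblinding had taken place.

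The cost is a few sentences, with no new participants, visits or data. The downside is that a nominal P<0.05 on sIgA or a quality-of-life scale can no longer be reported as a demonstrated effect.

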### **9.2 Sample Size Determination**

A preliminary study was conducted prior to the current study for sample approximation [10]. We screened 47 volunteers and excluded those who were pregnant or planning to become pregnant, extremely ill, immune

deficient, taking medications/supplements known to affect Protective Qi status, or who consumed more than 28 g alcohol per day (i.e., the equivalent of more than 24 ounces of beer, 10 ounces of wine, or 3 ounces of distilled alcohol daily). 30 participants diagnosed with PQD were enrolled and treated with  $\beta$ -glucan in a dose of ~200 mg/day for 8 weeks. The PQD status (severity score) was monitored biweekly and used to estimate the effect size of  $\beta$ -glucan. Last Observation Carried Forward (LOCF) [15] imputation was used for handling missing data. When analyzing the data, we used matching techniques [11] to create a virtual control group that is essentially equivalent to the treatment group on observed pre-intervention characteristics. Nonetheless, any potential confounders were regarded as the effectors of Regression To Mean (RTM) [12] and were accounted for by Trochim's method ([13], P322) that adjusts an individual's pre-test score as follows:

$$x_{adj} = \bar{x} + r(x_{pre} - \bar{x}_{pre})$$

Where  $x_{adj}$  is the adjusted pretest value,  $\bar{x}_{pre}$  is the treatment group pre-test mean,  $r$  is the pre-post correlation of the severity score for the treatment group, and  $x_{pre}$  is the original pretest value. We then used Cohen's  $d$  ([14], P276) to calculate the treatment effect size.

$$d = 2 * f = 2 * \sqrt{\frac{\frac{SS(x_{post} - x_{pre}),}{SS(x_{post})}}{1 - \frac{SS(x_{post} - x_{pre}),}{SS(x_{post})}}} = 2 * \sqrt{\frac{\frac{7.479}{7.479 + 4.928}}{1 - \frac{7.479}{7.479 + 4.928}}} = 2 * 1.23 = 2.46$$

Where  $x_{post}$  is the post-treatment severity score, SS is the sum of square, and  $f$  is the F test on means in the analysis of variance and covariance.

Given the Cohen's  $d$  is a positively biased estimator of effect size when sample size are small [14], we adjusted Cohen's  $d$  to conventional "large effect size (0.8)".

Assuming an allowable Type I error (alpha) of 0.01 and power value of 0.9, we performed R package "pwr" and obtained a minimal sample size of 49 for each group.

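### Two primary measures are each tested at two-sided 0.05 with no rule for what counts as success, and the sample size uses a different alpha (0.01)

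*Combined protocol and SAP*

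**What the plan says.** All references are to the combined protocol and SAP.

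- **Synopsis (1.1):** one primary endpoint, two methods: "The primary endpoint is the change of PQi Deficiency (PQD) status accessed by a standardized multifactorial severity score and traditional method".
- **Section 3:** the severity score and the traditional method are separate bullets under Primary. The justification column adds: "The traditional diagnosis method is also used as an additional way to evaluate the treatment".
- **Section 9.1:** a single primary line that does not choose between them: "Change of Protective Qi after a total of 12 weeks follow-up".
- **Section 9.4.2:** under "Other details analysis of the primary endpoints are described as follows" both measures are described, and for each the change from baseline is said to indicate the treatment effect. The score goes to a linear mixed regression, or to an aligned-rank ANOVA if assumptions fail. The effect on the diagnosis "will be analyzed using generalized mixed linear model [18] for conventional PQD diagnosis", and "The change of PQi status from baseline, indicating the treatment effect, will be calculated and analyzed by categorical statistic". The significance threshold is two-tailed 0.05 for all analyses.
- **Section 9.2:** the effect size comes from the severity score alone. The sample size starts from "Assuming an allowable Type I error (alpha) of 0.01 and power value of 0.9" and arrives at 49 per group.

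No section gives a success rule, a testing order or a multiplicity adjustment for the two PQD measures.

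**The concern.** With two primary measures, the plan has to say what happens when they disagree. There are three natural rules, and they differ in error and power:

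1. **Either suffices.** There are two chances at the primary claim, so its error exceeds 5%.
2. **Both required.** Error is at most 5%, but the trial is only as powerful as its weaker measure allows, and the diagnosis has no sample-size calculation.
3. **Score leads.** Error is at most 5%, and the sizing in 9.2 applies.

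As written, any of the three could be adopted after the results are known. Section 9.4.2 itself describes the diagnosis as a non-standardised, qualitative assessment, so an unadjusted route to a primary claim through it needs a written rule.

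The alpha mismatch adds a second ambiguity. A primary P value between 0.01 and 0.05 is significant under 9.4.2 but exceeds the Type I error that 9.2 calls allowable.

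**Working it through.** **Inputs from the documents.** Cohen's d = 0.8, alpha 0.01, power 0.90 and 49 per group (9.2); two-tailed 0.05 (9.4.2); 1:1 allocation (6.3); planned attrition 20% (7.2.2). The per-arm number is 62 in 4.1, while the synopsis has 130 in total, or 65 per arm at 1:1. Both are used.

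**Assumptions, because the documents give no figures.** The correlation between the two test statistics, the proportion still PQD on placebo, and the treatment difference on the diagnosis.

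**Step 1. Reproduce the plan's figure.** For a two-sample t-test with n per group, noncentrality = d × √(n/2) and df = 2n − 2. At n = 49: 0.8 × √24.5 = 3.96, df = 96. Power at two-sided 0.01 is 90.6%; at n = 48 it falls just short of 90%. So 49 reproduces, and the 0.01 acts as a two-sided level (one-sided 0.01 would need 43). Also 49 / (1 − 0.20) = 61.25, rounded up to 62, the figure in 4.1.

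**Step 2. Same inputs at the level actually tested.** At two-sided 0.05, d = 0.8 needs 34 per group for 90% power. Power for the score:

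| n per arm | alpha 0.05 | alpha 0.025 | alpha 0.01 |
|---|---|---|---|
| 49 | 97.5% | 95.2% | 90.6% |
| 62 | 99.3% | 98.5% | 96.5% |
| 65 | 99.5% | 98.9% | 97.3% |

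**Step 3. Error if either measure suffices.** For independent tests, 1 − (1 − 0.05)² = 0.0975. For correlated tests, error = 1 − P(|Z1| < 1.96 and |Z2| < 1.96) under a bivariate normal with correlation ρ:

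| ρ (assumed) | each at 0.05 | each at 0.025 |
|---|---|---|
| 0 | 9.75% | 4.94% |
| 0.5 | 9.1% | 4.65% |
| 0.8 | 7.8% | 4.0% |
| 0.9 | 7.0% | 3.6% |

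**Step 4. Error under the other rules.** If the score leads and the diagnosis is tested only afterwards, the error over both is at most 5%. If both are required and neither has an effect, error = 0.05 + 0.05 − (error in step 3): 0.25%, 0.9%, 2.2% and 3.0% at the four correlations. The upper limit is 5%, when one measure has a true effect.

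**Step 5. Power if both are required.** Joint power cannot exceed the power of the diagnosis. For a two-proportion test at two-sided 0.05, power = Φ[(δ − 1.96 × √(2p̄(1 − p̄)/n)) / √((p1(1 − p1) + p2(1 − p2))/n)]. Example with n = 62, 70% still PQD on placebo and 50% on active: p̄ = 0.60, so (0.200 − 1.96 × 0.0880) / 0.0861 = 0.32, and power is 62.5%. For a 20-point difference:

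| Placebo PQD (assumed) | n = 62 | n = 65 |
|---|---|---|
| 50% | 62.5% | 64.6% |
| 60% | 60.7% | 62.8% |
| 70% | 62.5% | 64.6% |
| 80% | 68.5% | 70.6% |
| 90% | 80.3% | 82.1% |

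Reaching 90% power at placebo rates of 50%, 70% and 90% needs differences of 27.5, 28.4 and 23.7 points with 62 per arm, or 26.9, 27.8 and 23.0 points with 65.

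These are single-visit t-tests and two-proportion tests, not the mixed models planned in 9.4.2. They show the order of magnitude only.

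**The case against.** The best counter-argument is that the plan already leans towards the score. The synopsis uses the singular, 9.1 has one primary line, section 3 calls the traditional method an additional way to evaluate treatment, and 9.2 sizes on the score alone. Nothing says that either measure suffices, and that is the only reading that inflates error. This stands as a fair account of the text's direction. It is not a decision rule: the additional-way remark sits in the Primary row itself, and 9.4.2 speaks of primary endpoints in the plural. No text says what follows if the score fails and the diagnosis succeeds.

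It is also fair that 9.75% is an upper case. Both measures rate the same construct, in the same participants, by the same type of assessor, so independence is implausible and 7% to 8% is more realistic if the correlation is high. The documents do not give the correlation.

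The power figures for the diagnosis rest on assumed rates and a simpler test than the planned model. They show that this measure was not sized, not that its power is inadequate.

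On alpha, 9.4.2 is explicit, and sizing at the stricter level only adds power. That limits the point to reconciling two sections.

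Two further points are separate and leave this one intact. Section 6.4 would censor participants with compliance below 80% or above 120%, which conflicts with the intention-to-treat approach in 9.3 and could shrink the analysed set. At 49 per arm, the step 5 calculation gives 51% to 70%. And the Table 2 items, with the Table 1 weights, have a maximum of about 3.3 (0.25×3 + 0.167×4 + 0.167×4 + 0.083×3 + 0.067×4 + 0.10×2 + 0.167×3), against a stated range of 1 to 5.

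**Conclusion.** The concern holds and should be fixed. The plan permits two unadjusted primary tests at two-sided 0.05 and does not define a positive trial. The false-positive rate of the primary claim is at most 5% if the score leads or both measures are required. It is 7.0% to 9.75% if either suffices, for assumed correlations from 0.9 down to 0. If both are required, power for the primary claim is capped by the diagnosis: 61% to 80% with 62 per arm and 63% to 82% with 65, for an assumed 20-point difference and placebo rates of 50% to 90%. The score has over 99% power at d = 0.8 and two-sided 0.05 with either number.

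The alpha mismatch is secondary. The 49 per group reproduces at two-sided 0.01, while 9.4.2 tests at 0.05, where 34 would do. The trial is not underpowered for the score, but the alpha and power in 9.2 do not describe the planned test.

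**What to change.** - Name the week-12 change in PQD severity score as the single primary endpoint in the synopsis, section 3, 9.1 and 9.4.2. This matches the timing in 9.1 and the sizing in 9.2.
- Test the traditional diagnosis only if the score is significant, at the same alpha. This holds the error over both measures at that alpha.
- State one two-sided alpha in 9.2 and 9.4.2: either restate 9.2 at 0.05 or test at 0.01. Section 9.4.2 as written says 0.05, but the documents do not show why 9.2 differs.
- If the sponsor wants either measure to count, test each at 0.025 instead. The error is then at most 5%, and the score keeps 95.2%, 98.5% and 98.9% power with 49, 62 and 65 per arm.
- Record whether these choices preceded unblinding. Version 4.0 is dated February 2022, and section 5.5 planned enrolment to end in March 2019. If the choices came later, say so, report both PQD measures in full, and give the primary result against both 0.05 and 0.01. In that case the remedy is disclosure rather than error control.

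The cost is wording in five places, with no added participants or visits. The downside is that the traditional diagnosis cannot support a claim if the score fails.

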## **8. Study Assessments and Procedures**

### **8.1 Efficacy Assessments**

The efficacy of Proglucamune® on PQi and GQi status will be quantified as outlined in the PQD scoring system (Table 1 & Table 2) and the GQ scoring system (Table 3 & Table 4). Each subject's PQi and GQi status – as reflected in their PQD and GQD score – for each visit will be used to determine whether or not the subject's PQi or GQi status is improved by Proglucamune®. Treatment efficacy will also be evaluated by measuring and comparing salivary IgA levels at day 1 (Study Visit 1), day 42 (Study Visit 4) and day 84 (Study Visit 7).

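### Salivary IgA is planned as an untransformed change with an undefined switch to ranks; a pre-specified log-scale model with baseline adjustment gives one estimable effect and, if secretion is skewed, more power

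*Combined protocol and SAP*

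**What the plan says.** In the combined protocol and SAP, the sIgA bullet of section 9.4.2 reads: "The effect of Proglucamune on the participants' immunity will be assessed by the change of saliva secretary IgA". The unit given there is µg/min, a rate of secretion. The bullet then describes the analysis: "The change of the score from baseline, indicating the treatment effect, will be calculated and analyzed by statistical means". The bullets for the PQD, GQD and Global Health scores end with the same sentence. Section 8.1 sets three measurement times, days 1, 42 and 84: "Treatment efficacy will also be evaluated by measuring and comparing salivary IgA levels at day 1".

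The general paragraph of 9.4.2 covers all continuous outcomes. They "will be evaluated by skewness and kurtosis for normality". If both measures lie within ±2 the outcome is summarised by a mean with 95% CI, otherwise by a median with 95% CI. The model is linear mixed regression, "or Aligned Rank Transformation ANOVA [17] if assumptions of the regression model were not satisfied". No criterion is given for that switch, and the ±2 rule is tied only to the choice of summary. Testing is two-sided at 0.05.

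Neither place mentions a log scale, a ratio or baseline sIgA as a covariate. No mean, SD, correlation, expected effect or power is given for sIgA.

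**The concern.** A secretion rate is positive, and quantities of that kind are often right-skewed, with a spread that grows with the level. If sIgA behaves in this way, an untransformed change gives most weight to participants with high secretion. The plan's only protection is a rank analysis, and that has two drawbacks here. First, nobody can tell in advance whether it will be used, because the assumptions to be checked and the threshold for failure are not stated. Second, an aligned-rank ANOVA yields a test without an effect in µg/min or per cent. The medians by arm that the plan would report are not the quantity tested.

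sIgA is the only laboratory measure among the efficacy endpoints (sections 3 and 8.1), and 9.4.2 uses it as the measure of the effect on immunity. A reader will want to know by how much secretion differed between arms. At stake are that estimate and some power for one secondary endpoint.

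**Working it through.** **The plan's own figure.** The only sample size calculation (section 9.2) concerns the primary endpoint: d = 0.8, alpha 0.01, power 0.9. A two-sided two-sample t-test needs 48.19, so 49 per group, as stated. With the planned 20% attrition (section 7.2.2), 49/(1 − 0.20) = 61.25, so 62, the number in section 4.1. There is no sIgA figure to reproduce.

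**Inputs.** From the documents: 62 per arm, 1:1 allocation (section 6.3), two-sided 0.05. Assumed, because the documents are silent: log-normal secretion, a true multiplicative effect of +30%, log-SD σ of 0.4 to 1.0, correlation r between log baseline and log follow-up of 0.5 and 0.7, and one follow-up value. With CV = √(exp(σ²) − 1), these σ correspond to CVs of about 0.42, 0.66, 0.95 and 1.31.

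**Log-scale analyses in closed form.** Power ≈ Φ(ln 1.3 / SE − 1.96), where
- log change: SE = σ √(2(1 − r)) √(2/62)
- log follow-up with log baseline as covariate: SE = σ √(1 − r²) √(2/62)

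Example, σ = 0.8 and r = 0.5: ln 1.3 = 0.2624 and √(2/62) = 0.1796.
- Log change: SE = 0.8 × 1 × 0.1796 = 0.1437; 0.2624/0.1437 − 1.96 = −0.13; power 45%.
- With covariate: SE = 0.8 × 0.866 × 0.1796 = 0.1244; 0.2624/0.1244 − 1.96 = 0.15; power 56%.

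**Raw change and the plan with its fallback, by simulation** (4,000 trials per cell). The fallback is represented by a t-test on raw change if skewness and excess kurtosis of the week-12 values are both within ±2, otherwise a rank test on change. This needs two further assumptions: that the ±2 rule triggers the switch, and that a rank test on change stands in for the full aligned-rank model.

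Power in per cent, r = 0.5 / r = 0.7:

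| log-SD | Raw change, no fallback | Plan with rank fallback | Log change | Log with baseline covariate |
|---|---|---|---|---|
| 0.4 | 94 / 99.5 | 96 / 99.6 | 95 / 99.6 | 98.8 / 99.9 |
| 0.6 | 62 / 80 | 66 / 84 | 68 / 87 | 80.3 / 92.6 |
| 0.8 | 33 / 48 | 40 / 58 | 44 / 64 | 55.9 / 72.5 |
| 1.0 | 20 / 29 | 28 / 41 | 31 / 47 | 39.2 / 53.4 |

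The first three columns are simulated. The plan's entries at log-SD 0.4 come from a separate run in which log change gave 96 / 99.5. The last column is the closed form; simulation gave 80 / 91, 54 / 71 and 38 / 53 for the lower three rows, at most about 2 points lower.

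**Differences.**
- Log change minus plan with fallback: about 0 at log-SD 0.4; 2 / 3 at 0.6; 4 / 6 at 0.8; 3 / 6 at 1.0.
- Log change minus raw change without fallback: 1 / 0.1, 6 / 7, 11 / 16, 11 / 18. A repeat of the last cell gave 29% v 46%, a difference of 17.
- Log with covariate minus plan with fallback: 2.8 / 0.3, 14.3 / 8.6, 15.9 / 14.5, 11.2 / 12.4.
- The part of that due to baseline adjustment at log-SD 0.6 to 1.0 (closed form with covariate minus closed-form log change of 68.2 / 88.2, 44.7 / 65.4, 30.9 / 47.0): 12.1 / 4.4, 11.2 / 7.1, 8.3 / 6.4.

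**Screen and type I error.** The ±2 screen passes in about 56%, 21%, 5% and 1% of such trials at log-SD 0.4, 0.6, 0.8 and 1.0. Under no effect, rejection rates were 4.5% to 5.4% for every method.

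**The case against.** The plan is not defenceless against skew. The general paragraph of 9.4.2 applies to sIgA, and a rank analysis removes the pull of a few high secretors. A reader might infer that the plan gives up as much as 18 points of power, or that extreme values would dominate the result. That holds only against raw change with no fallback, at log-SD 1.0 and correlation 0.7. In that cell the ±2 screen fails about 99% of the time, so under the assumption that failure triggers ranks, the plan would almost always have moved to them. Against the plan with its fallback, the log transformation alone gains 0 to 6 points. This part of the objection stands.

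Two other inferences also go too far. One is that the screen passes or fails by chance: it is close to an even split only near log-SD 0.4, where raw and log analyses have the same power. The other is that no summary would remain: medians with 95% CI are planned.

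It can also be said that the log-normal, multiplicative model favours the log analysis by construction, that the effect and spread are assumed, that an arithmetic change is only the natural reading of a loosely worded sentence, and that the endpoint is secondary. All true, and they limit how much weight the power figures can carry. They do not supply what is missing: a stated criterion for leaving the mixed model, and a between-arm estimate when ranks are used.

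**Conclusion.** The point holds in a limited form. As written, the scale and test for sIgA depend on an undefined check of the data, and on the rank branch there is no between-arm effect to report. A pre-specified log-scale model removes both problems.

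The power argument is secondary and conditional. Under the assumptions above, the log scale by itself is worth about 0 to 6 points over the plan with its fallback. Log scale plus baseline covariate is worth about 8 to 16 points at log-SD 0.6 to 1.0 and 0 to 3 at log-SD 0.4, with much of the larger gain due to the covariate. Only 62 per arm and two-sided 0.05 come from the documents, and right skew is likely rather than shown. The calculations use one follow-up visit and a simplified stand-in for the rank model.

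A reader might infer from the data-dependent choice that false positives are inflated. The checks do not show that: type I error stays near 5%. sIgA enters neither the primary analysis nor the sample size, so the primary result is untouched.

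**What to change.** In the sIgA bullet of section 9.4.2, replace the analysis of raw change with text such as:

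*sIgA secretion rate will be log-transformed before analysis. A linear mixed model will be fitted to log sIgA at days 42 and 84 with treatment, visit, treatment-by-visit and baseline log sIgA as covariate. The effect will be reported as the week-12 ratio of geometric means (Proglucamune/placebo) with 95% CI.*

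State that for this endpoint any rank analysis is a sensitivity analysis and that the ±2 rule does not select the primary method. Add a substitution rule for zero or below-limit values, fixed before the data are seen.

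The cost is SAP wording only, with no new visits or samples. The effect becomes a ratio rather than a difference in µg/min, and the substitution rule is one more thing to define. Timing matters: version 4.0 is dated February 2022 while section 5.5 plans enrolment from December 2018 to March 2019. If sIgA results by arm have already been seen, the log analysis should be labelled post hoc.
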